8.2 Administration of experimental and control interventions

As no prescription drugs and only minimally invasive methods are used, the experiment is not discussed further in chapters 8.2-8.4 and reference is made to Chapter 9.

8.2.1 Experimental Intervention

Cold water immersion

Test subjects in this group are asked to take a cold water bath after carrying out the jump protocol. The application lasts 10 minutes (and is repeated after 2 hours) at a water temperature of 10°C. In a sitting position, the water level must reach the sternum.

Hot water immersion

Test subjects in this group are asked to take a hot water bath after carrying out the jump protocol. The application lasts 10 minutes (and is repeated after 2 hours) at a water temperature of 40°C. In a sitting position, the water level must reach the sternum.

In all experimental interventions, an examiner is located directly next to the test person for monitoring at all times.

8.2.2 Control Intervention

Hypoxia group

The subjects of the hypoxia group will perform the jump protocol under hypoxia, which is generated with the Cloud 9. This intervention is used to determine the physiological effect under hypoxic conditions.

Control group

The test subjects of the control group are in our laboratory and are asked to lie on their back for 10 minutes after completing the jump protocol.

During all control interventions, an examiner is located directly next to the test person for monitoring at all times.

8.3 Dose / Device modifications

All participants will be treated with the same duration or dosage within their group.

8.4 Compliance with study intervention

The test subjects are only motivated to perform MVIC and the jump height measurement in order to keep their compliance high. The rest of the communication is kept to a minimum. Only study-related conversations are conducted in order not to influence the psychophysiological effects and to ensure homogeneity.

8.5 Data Collection and Follow-up for Withdrawn Participants

If consent is withdrawn, the data and samples already collected must be included in the analysis for scientific and safety reasons. These are only anonymised after the analysis (Art. 9 ClinO).

SUPSI

There is no disadvantage for the participants if they discontinue their participation in the study and no further interventions are necessary for follow-up treatment.

If study participation was discontinued due to a reaction occurring during study participation, this will be recorded and reported to the sponsor investigator (head of the research laboratory), study director and supervisor of the study. If medical treatment is required, the report will be forwarded to the business liability insurance of Thim van der Laan AG (Basler Versicherung) to ensure the appropriate follow-up treatment.

8.6 Trial specific preventive measures

The questionnaire asks about the intake of medication. In addition, the test subjects agree to undergo a pregnancy test (urine test) by signing the consent form. This test is handed over, explained, received and interpreted by the head of the study ([name]). They do not have to pay any costs for it – the test is provided to them free of charge. A positive pregnancy test leads to the exclusion of this study. Only the principal investigator, the study supervisor and authorised persons of the ethics committee can view this test result. No one else will know the result of this test. If deviations in the statics are visible but not medically diagnosed, the study director reserves the right to measure them (leg length difference, scoliosis angle) and to exclude test subjects from participation.

8.7 Concomitant Interventions (treatments)

No further side effects are expected as a result of participation in the study.

8.8 Study Drug / Medical Device Accountability

The experiments take place exclusively in the research laboratory of the University of Applied Sciences and Arts of Southern Switzerland, Physiotherapy Graubünden, in Landquart. This means that there is no transport of the products and measuring devices used. There is therefore no liability for the transport of the product.

8.9 Return or Destruction of Study Drug / Medical Device

The Cloud 9, as well as the two Aspen whirlpools, were acquired by the research department of the "University of Applied Sciences and Arts of Southern Switzerland" and will remain in the research laboratory after completion of the measurements.

SUPSI

9. STUDY ASSESSMENTS

9.1 Study flow chart(s) / table of study procedures and assessments

The test subject information is sent to the test subjects' homes in advance or given to them personally

1. Subject Information & Informed Consent

30 min (questions and ambiguities will be discussed individually)

2. Preparation of the test person

15 min

3. Executing the test protocol

SUPSI

Test protocol: Time required – maximum 255 min			
Cold Water Immersion vs. Hot Water Immersion vs. Hypoxia Group vs. Passive Control Group			
Cold water immersion 1.) Baseline Informed consent, written consent, review of inclusion/exclusion criteria, health questionnaire, pregnancy test Heart rate Skin/ core body temperature Oxygen saturation (blood, muscle) Inflammation parameters VAS & BORG thermal comfort and thermal sensation US 3 x Vertical Jumps 3 x MVIC =30 min	Hot water immersion 1.) Baseline Informed consent, written consent, review of inclusion/exclusion criteria, health questionnaire, pregnancy test Heart rate Skin/core body temperature Oxygen saturation (blood, muscle) Inflammation parameters VAS & BORG thermal comfort and thermal sensation US 3 x Vertical Jumps 3 x MVIC =30 min	Hypoxia Intervention 1.) Baseline Informed consent, written consent, review of inclusion/exclusion criteria, health questionnaire, pregnancy test Heart rate Skin/core body temperature Oxygen saturation (blood, muscle) Inflammation parameters VAS & BORG thermal comfort and thermal sensation US 3 x Vertical Jumps 3 x MVIC =30 min	Passive Control Intervention 1.) Baseline Informed consent, written consent, review of inclusion/exclusion criteria, health questionnaire, pregnancy test Heart rate Skin/core body temperature Oxygen saturation (blood, muscle) Inflammation parameters VAS & BORG thermal comfort and thermal sensation US 3 x Vertical Jumps 3 x MVIC =30 min
2.) Jump protocol 5 x 20 max vertical jumps after 30sec Heart rate Skin/ core body temperature	2.) Jump protocol 5 x 20 max vertical jumps after 30sec Heart rate Skin/ core body temperature	2.) Jump protocol under hypoxia 5 x 20 max vertical jumps after 30sec Heart rate Skin/ core body temperature	2.) Jump protocol 5 x 20 max vertical jumps after 30 sec Heart rate Skin/ core body temperature

SUPSI

Oxygen saturation (blood, muscle) Mod. BORG & BORG =30 min	Oxygen saturation (blood, muscle) Mod. BORG & BORG =30 min	Oxygen saturation (blood, muscle) Mod. BORG & BORG =30 min	Oxygen saturation (blood, muscle) Mod. BORG & BORG =30 min
3.) Cold water immersion 10 min at 10°C Heart rate Skin/core body temperature Oxygen saturation (muscle) Thermal comfort and Temperature sensation =10 min	3.) Hot water immersion 10 min at 40°C Heart rate Skin/core body temperature Oxygen saturation (muscle) Thermal comfort and Temperature sensation =10 min	3.) Passive supine position 10 min at room temperature Heart rate Skin/core body temperature Oxygen saturation (muscle) Thermal comfort and Temperature sensation =10 min	3.) Passive supine position 10 min at room temperature Heart rate Skin/core body temperature Oxygen saturation (muscle) Thermal comfort and Temperature sensation =10 min
4.) Follow-up immediately after the intervention Heart rate Skin/core body temperature Oxygen saturation (blood, muscle) Inflammation parameters US VAS & BORG 3 x Vertical Jumps 3 x MVIC =30 min	4.) Follow-up immediately after the intervention Heart rate Skin/core body temperature Oxygen saturation (blood, muscle) Inflammation parameters US VAS & BORG 3 x Vertical Jumps 3 x MVIC =30 min	4.) Follow-up immediately after the intervention Heart rate Skin/core body temperature Oxygen saturation (blood, muscle) Inflammation parameters US VAS & BORG 3 x Vertical Jumps 3 x MVIC =30 min	4.) Follow-up immediately after the intervention Heart rate Skin/core body temperature Oxygen saturation (blood, muscle) Inflammation parameters US VAS & BORG 3 x Vertical Jumps 3 x MVIC =30 min

SUPSI

5.) Cold water immersion 10 min at 10°C Heart rate Skin/core body temperature Oxygen saturation (muscle) Thermal comfort and thermal sensation =10 min	5.) Hot water immersion 10 min at 40°C Heart rate Skin/core body temperature Oxygen saturation (muscle) Thermal comfort and thermal sensation =10 min		
6.-8.) Follow up 24, 48 and 72 hours after the intervention Heart rate Skin/ core body temperature Oxygen saturation (blood, muscle) Inflammation parameters US VAS & BORG 3 x Vertical Jumps 3 x MVIC =30 min per follow-up	6.-8.) Follow up 24, 48 and 72 hours after the intervention Heart rate Skin/ core body temperature Oxygen saturation (blood, muscle) Inflammation parameters US VAS & BORG 3 x Vertical Jumps 3 x MVIC =30 min per follow-up	5.-7.) Follow up 24, 48 and 72 hours after the intervention Heart rate Skin/ core body temperature Oxygen saturation (blood, muscle) Inflammation parameters US VAS & BORG 3 x Vertical Jumps 3 x MVIC =30 min per follow-up	5.-7.) Follow up 24, 48 and 72 hours after the intervention Heart rate Skin/core body temperature Oxygen saturation (blood, muscle) Inflammation parameters US VAS & BORG 3 x Vertical Jumps 3 x MVIC =30 min per follow-up

SUPSI

Test protocol	Time exposure	Visits
Information, written consent, examination of inclusion/ exclusion criteria, health questionnaires, pregnancy test, detection of adverse events	30min + 15min	Unique
Baseline, recording of adverse events	30min	Unique
Jump log, recording of adverse events	30min	Unique
Cold water immersion, recording of adverse events	20min + 130min (3x30min) = 150min	Unique
Hot water immersion, recording of adverse events	20min + 130min (3x30min) = 150min	Unique
Hypoxia group, recording of adverse events	20min + 120min (3x30min) = 140min	Unique
Control group, recording of adverse events	20min + 120min (3x30min) = 140min	Unique
Total time spent	245min or 255min	

SUPSI

9.2 Assessments of outcomes

The following data are collected during all tests described in the sub-protocols in chap. 9.1.

9.2.1 Assessment of primary outcome

Jump height measurement

The jump height after exercise is determined using a jump height measuring plate designed for this purpose (Just Jump Plate, Probatics Inc., Huntsville, USA). The test subjects assume a standing position on the plate. They are allowed to start from the squatting position to measure the jump height (countermovement jump). The arms must be placed at the hips during the entire movement. The measurement moments take place directly, 24 hours, 48 hours and 72 hours after the intervention.

Muscle activity (MVIC)

MVIC is performed on the Cor 1 – ergometer chair for biomechanical measurements V1.0 and is given in kg (www.otbioelettronica.it). The conduction velocity is measured with the help of the surface electromyogram system EMG-USB2 from OT Bioelettronica (otbioelettronica.it), bandpass filtered between 10-750Hz and rectified (full-wave rectify). MVIC is measured on the Cor 1 ergometer chair in 90° knee flexion. The raw data of muscle activity to measure conduction velocity is processed using OT Bioelettronica's (MISO II) software. The electrodes are placed according to the guidelines of Barbero et al. (2012) "Atlas of Muscle Innervation Zones". The EMG electrodes are placed on the front of the thigh and on the tibia. These areas must be shaved if there is too much hair. The measurement takes place immediately, 24 hours, 48 hours and 72 hours after the intervention.

Muscle swelling

Muscle swelling of the thigh is measured by ultrasound imaging (MyLabClassC, Esaote, Genoa, Italy). The images are analysed with the OsiriX DICOM viewer software (OsiriX, Pixmeo SARL, Switzerland). The measurements are taken before, immediately, 24 hours, 48 hours and 72 hours after the intervention.

Oxygen saturation of the blood

The oxygen saturation of the blood is measured with a portable pulse oximeter with a finger clip probe (Nonin 7500, Nonin medical B.V., Plymouth, USA). This measurement takes place during the baseline measurements as well as during the jump protocol.

Oxygen saturation of the muscle

The oxygen saturation (%) of the thigh muscles is measured using the tissue oxygenation monitor using near-infrared spectroscopy (moorVMS-NIRS, moor instruments, www.moor.co.uk). The measurement is non-invasive and takes place using near-infrared light. The sensors are fixed around the corresponding muscles. The oxygen saturation measurement is taken directly and 24, 48 and 72 hours after the intervention.

Heart rate

The heart rate is determined using a heart rate monitor with a chest strap (Polar T31, Polar Inc. Kempele, Finland). Blood pressure and heart rate are measured directly and 24, 48 and 72 hours after the intervention.

Skin temperature

Skin temperature is measured via the iButton system (www.ibuttonlink.com). The self-adhesive sensors transmit the information about the skin temperature wirelessly to a computer. Furthermore, the skin temperature is recorded using a thermal imaging camera (A655 sc series, FLIR, InfrarotTec Systems, Ranstadt, Germany). The skin temperature is measured directly and 24, 48 and 72 hours after the intervention. The iButtons are applied with a tape strip to the following areas: centre of the shoulder blade, neck (6th cervical vertebra), back of the hand, centre of the shin, and centre of the thigh. The iButtons are removed from the affected areas during the cold water bath or hot water bath and then reattached.

SUPSI

Core Body Temperature

The core body temperature is determined via the e-Celsius® performance (<https://www.bodycapmedical.com>). With the help of this ingestible capsule, the core body temperature is continuously monitored, recorded and transmits the data wirelessly to a monitor (BodyCAP medical, Hérouville Saint-Clair, France). Core body temperature is measured directly and 24, 48 and 72 hours after the intervention.

Inflammation parameters

The measurement of inflammatory parameters such as creatine kinase, interleukin 6 or C-reactive protein (CRP) is carried out via a venous blood sample of approx. 6ml (Accutrend, Roche Diagnostic, Rotkreuz, Switzerland & Reflotron, Roche Diagnostic, Rotkreuz, Switzerland). The measurement is carried out immediately, 24 hours, 48 hours and 72 hours after the intervention by trained specialists.

Subjective information on shortness of breath

The subjects reported their subjective feeling of shortness of breath on a modified BORG scale (0 – 10). The scale will be scaled from "0" (no shortness of breath at all) to "10" (maximum breathlessness). The measurement takes place before the intervention.

Subjective information on general exhaustion

The subjects reported their subjective general feeling of exhaustion on a BORG scale (6 – 20). The scale will be scaled from "6" (very, very light load) to "20" (very, very strenuous load). The measurement takes place before the intervention.

Subjective muscle soreness

The test subjects reported their subjective feeling of muscle soreness on a visual analogue scale (VAS). The scale will be scaled from "0" (no muscle soreness present) to "10" (largest imaginable muscle soreness) in cm increments. The measurement moments take place directly, 24 hours, 48 hours and 72 hours after the intervention.

Thermal comfort and temperature sensation

This parameter is measured using a scale. The test subjects indicate their subjective temperature perception on a 9-point scale from -4 (very cold) to +4 (very hot). They then rate the thermal comfort from 0 (pleasant) and 4 (extremely unpleasant) on a 5-point scale. These measurements are taken before and after the intervention.

9.2.2 Assessment of secondary outcomes

None available.

9.2.3 Assessment of other outcomes of interest

None available.

9.2.4 Assessment of safety outcomes

No corresponding parameters are collected.

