5.4 Safety Outcomes

No further outcomes are included that serve the purpose of safety.

Discontinuation of the experiment is the responsibility of the examiners with regard to the subject's resilience. If this is judged to be too low, the examiner can stop the experiment.

If the test subject does not feel well according to her own subjective assessment, she can stop the experiment and withdraw participation in the study. If the cold application is unacceptable for the test subject, she can discontinue the application. She will not suffer any disadvantages as a result.

The current regulations of the Canton of Graubünden and those of the FOPH for protection against the coronavirus will be taken into account and implemented when conducting the study.

SUPSI

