7.4 Criteria for withdrawal / discontinuation of participants

If a participant withdraws from the study, the allocation lot is returned to the pot in a new envelope and a new participant is sought.

The already completed consent form is kept in the locked filing cabinet. If consent is withdrawn, the data and samples already collected must be included in the analysis for scientific and safety reasons. These will only be anonymised after the analysis (Art. 9 ClinO).

The conditions for discontinuing the trial were described in chap. 5.4. There is no disadvantage for the participants if they discontinue their participation in the study.

SUPSI

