11.3 Statistical criteria of termination of trial

Only data from subjects who have completed the entire protocol will be included in the study. This ensures that all data has been collected under the same conditions and thus remains homogeneous and comparable.

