11.4.5 Safety analysis

-

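### The 9.1 table records adverse events at each procedure, but 9.2.4 says no safety parameters are collected, 11.4.5 is blank, and section 11 excludes data that 7.4 and 8.5 require to be analysed

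*Combined protocol and SAP*

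**What the plan says.** **Collection.** The summary table of time and visits at the end of section 9.1 puts adverse-event recording in each row: "Baseline, recording of adverse events", "Jump log, recording of adverse events", "Cold water immersion, recording of adverse events", and likewise for the hot water, hypoxia and control rows. The information and consent row has adverse-event detection as well. The detailed arm-by-arm flow chart in the same section does not list adverse events at any step.

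Section 9.2.4 says: "No corresponding parameters are collected". Subsections 9.2.4.1 (adverse events), 9.2.4.2 (laboratory parameters) and 9.2.4.3 (vital signs) each contain a dash. Section 5.4 says: "No further outcomes are included that serve the purpose of safety".

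**Analysis.** Section 11.4.5, safety analysis, is a dash. Section 11.3 says: "Only data from subjects who have completed the entire protocol will be included in the study". Section 11.4.1 admits complete data sets only, and 11.5 keeps a non-completer's data but leaves them out of the final analysis.

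**Withdrawal.** Sections 7.4 and 8.5 say that, when consent is withdrawn, "the data and samples already collected must be included in the analysis for scientific and safety reasons".

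**Reporting.** Section 8.5 requires a discontinuation caused by a reaction to be recorded and reported, and 9.2.5 requires the same for an injury. Section 10.2 defines adverse and serious adverse events, asks for causality and severity assessments, and sets a 24-hour limit for reporting serious events to the sponsor-investigator. Section 10.3 requires an annual safety report.

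**The concern.** Three things do not fit together. Events are to be recorded, yet the section that should say how they are assessed says nothing is collected. No analysis of the recorded events is specified anywhere. The only analysis set that is defined leaves out anyone who stops early, although two other sections require some of those participants' data to be analysed, with safety as one of the stated reasons.

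At stake is whether the trial can give a plain account of tolerability by arm. Section 3.7 names headache, loss of consciousness, disorientation and nausea as possible under hypoxia. Section 5.4 foresees participants stopping because the cold application is unacceptable, and examiners stopping the experiment. Section 3.1 aims at recommendations on thermotherapy. A reader of those recommendations would expect to see how many participants in each arm had an adverse event and how many stopped because of one.

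**Working it through.** This is mainly a reading check, with a short calculation for scale.

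**Step 1: is collection specified?** The 9.1 summary table says yes. Section 9.2.4 says no, and 9.2.4.1 is empty. Even if 9.2.4 means only that there is no dedicated safety endpoint, the subsection headed adverse events still does not say what is recorded, when or how.

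**Step 2: is an analysis specified?** Section 11.4.5 is a dash, and 11.4.3 offers no secondary analyses. No recorded adverse event has a planned analysis, whether it occurs in a completer or a non-completer.

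**Step 3: whose data may be analysed?** There are three cases.

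- A participant completes: she is in the analysis set.
- A participant withdraws consent: 7.4 and 8.5 require her data to be analysed, while 11.3, 11.4.1 and 11.5 exclude them. Following section 11 breaches 7.4 and 8.5.
- A participant stops, or is stopped by the examiner, without withdrawing consent: 7.4 and 8.5 are silent on analysing her data, so section 11 alone applies and she is excluded.

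**Step 4: does reporting fill the gap?** Sections 8.5, 9.2.5, 10.2 and 10.3 ensure that such events are documented and passed on. The items listed in 9.2.5 are date and time, course, people involved, study ID and personal details; study arm is not among them. None of these sections asks for a summary by arm.

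**Step 5: how many participants could the completer rule exclude?** Inputs from section 11.2: 33 evaluable participants, 20% loss, 40 planned.

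- Reproducing the plan's figure: 33 × 1.20 = 39.6, rounded up to 40. (Dividing instead, 33 / 0.80 = 41.25, gives 42; the difference does not affect this point.)
- Planned loss: 0.20 × 40 = 8. Section 6.1 gives 60 instead, and the same 20% would be 0.20 × 60 = 12.
- The 20% covers both drop-out and incomplete data sets, so 8 or 12 is the whole allowance, not a forecast of adverse-event withdrawals.

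**Step 6: how likely is at least one such withdrawal?** The documents give no risk of adverse-event withdrawal and no allocation ratio. Assume equal arms (40 / 4 = 10 or 60 / 4 = 15) and a risk p per participant. The chance of at least one in an arm of n is 1 − (1 − p)^n.

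| Assumed p | n = 10 | n = 15 |
|---|---|---|
| 5% | 1 − 0.95^10 = 40% | 1 − 0.95^15 = 54% |
| 10% | 1 − 0.90^10 = 65% | 1 − 0.90^15 = 79% |
| 20% | 1 − 0.80^10 = 89% | 1 − 0.80^15 = 97% |

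So the conflict could well arise in practice even at a modest risk. The risks are assumptions chosen to show a range.

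**The case against.** The strongest reply is that 9.2.4 means only that there is no dedicated safety endpoint. It sits under safety outcomes and matches 5.4. On that reading it does not deny the recording in 9.1, and events that end participation are handled by 8.5, 9.2.5 and section 10. This is a fair reading of one sentence, and the reporting duties are real. It does not fill the dash at 9.2.4.1 or at 11.4.5, and it does not touch the conflict between section 11 and sections 7.4 and 8.5.

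Four stronger readings are tempting, and the documents do not support them.

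- *Harms that cause withdrawal are lost.* They are not. They are recorded and reported to the sponsor side, and to the ethics committee where section 10 requires it. What is missing is a planned tabulation.
- *The safety comparison between arms is biased by counting completers only.* No safety comparison is planned, so there is none to bias. Events in completers are untabulated too. The defect is an omission together with contradictory rules.
- *All participants who stop are covered by 7.4.* That section speaks only of withdrawn consent, and 5.4 separates stopping an application from leaving the study.
- *The completer rule prevents early termination for harm under 10.5.* That decision can draw on the continuing reports in 10.2 and 10.3, not on the final data set.

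It is also fair to note that recording at each procedure rests on the summary table alone, since the detailed flow chart does not mention it.

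**Conclusion.** The point holds: the plan is wrong as written. The recording in 9.1 is not carried through to 9.2.4, 9.2.4.1 or 11.4.5. Sections 11.3, 11.4.1 and 11.5 contradict 7.4 and 8.5 on data collected before consent is withdrawn. Followed literally, section 11 breaches the plan's own requirement and leaves anyone who stops because of an intervention outside every analysis by arm, although her event is documented and reported.

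The group exposed to this rule is up to 8 of 40 on the plan's own allowance, or 12 of 60 if the same 20% is applied to the number in section 6.1. The share due to adverse events cannot be derived from the documents. The contradiction does not depend on these figures; it is there in the text whatever the number of withdrawals. The planned efficacy analysis is a separate matter, and nothing here shows that it is biased.

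**What to change.** 1. In 9.2.4 and 9.2.4.1, state that adverse events are recorded at each step listed in 9.1, and add the recording to the detailed flow chart so that the two parts of 9.1 agree.
2. In 11.4.5, specify one descriptive table by arm giving the number and percentage of participants with any adverse event, and with discontinuation due to an adverse event. The denominator is all randomised participants, whether or not they finish.
3. Show events before and after the start of the jump protocol separately. Baseline already includes blood sampling, jumps and maximal contractions, while hypoxia exposure begins with the jump protocol and the baths follow it.
4. Exempt this table from 11.3, 11.4.1 and 11.5, and reconcile those three sections with 7.4 and 8.5 on what happens to data from participants who withdraw consent or stop for another reason.
5. In the same edit, reconcile 7.4, which returns the lot and seeks a new participant, with 11.4.1, which says no replacement is sought. If replacements occur, both the original and the replacement participant belong in the safety denominator.

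The cost is one descriptive table and a few sentences. It needs no new measurement and no change to sample size or conduct, because the events are already due to be recorded.
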